2.13.1.2 Preference

This domain consists of 3 items (**item 10, item 11 and item 20**). **Item 10** will assess “what type of medication did your child like the best”. **Item 11** will assess “the reason of preference for crushed medicine”. **Item 20** will capture the rank of the medicine based on whatever the children prefer. These item are to be considered a single items and the responses will be presented descriptively using frequency counts.

2.13.1.3 Concerns

Similar to adherence domain, concerns will be captured 2 ways:

1. based on the child’s perspective (**Item 1 and 2**) and
2. also based on the caregiver’s perspective (**Item 12**)

The concerns domain for the child’s perspective has 2 items which focus on “limiting child’s activity” (**Item 1**) and “getting upset about the side-effects” (**Item 2**). Both the items are measured using a 5-point response scale from “Always” =1 (worst), “Most of the time” =2, “Sometimes” =3, “Rarely” =4, and “Never” =5 (best); and a sum of scores for a Concerns domain for the child’s perspective will be created if both items are non-missing. A higher score will indicate lesser concerns.

There is only a single item to capture concern in regards to caregiver’s perspective. The **item 12** captures about “how worried whether the child is swallowing enough medication” and is scored on a 5-point response scale from “Always” =1 (worst), “Most of the time” =2, “Sometimes” =3, “Rarely” =4, and “Never” =5 (best). A higher score on the single item domain will indicate lesser caregiver concern.

For the mSICT questionnaire, the score for each domain (adherence and concerns) will be the mean of the score of items included in the corresponding domain. Note that for these domains, child’s perspective and caregiver’s perspective will be summarized separately. Standard descriptive analyses will be performed for each domain (adherence and concerns) score at screening visit 1 (baseline), week 4, week 12, and end of treatment visits, as well as their changes from baseline at week 4, week 12, and end of treatment for pre-treated chelation patients where baseline evaluation is available. For the Chelation naïve patients and patients treated with chelation therapy other than deferasirox who stopped chelation treatment more than 7 days prior to Screening visit, only descriptive statistics by visit will be provided. The standard descriptive analyses include: n, mean, standard deviation, minimum, median, and maximum. The 95% confidence intervals will be presented for the changes in mean from baseline for all domains at week 4 and week 12 and EOT for patients pre-treated with deferasirox only.

Box plot will be presented to summarize the scores graphically for each domain at week 4, week 12 and EOT.

All preference items will be analyzed descriptively by visit.

2.13.2 Palatability questionnaire

Like mSICT questionnaire, the palatability questionnaire will be completed at screening visit 1, week 4, week 12, and EOT. The responses at screening visit 1 for palatability questionnaire will be considered as baseline. The palatability questionnaire consists of 4 items. Two items measure the taste (**Item 1**) and aftertaste (**Item 2**) of the medication and are scored on a 5-point response scale with the response format “Very good” =1 (best), “Good” =2, “Neither good nor bad” =3, “Bad” =4, and “Very bad” =5 (worst).

The aftertaste item will be treated as an independent item (and will not be part of the scoring) and will be presented descriptively using frequency counts.

A summary of **items 1, 3 and 4** will be constructed using the following rules:

Recode item 1

“Very good”, “Good” & “Not good or bad” =1
“Bad” & “Very bad” = 2

Recode item 3

“Swallowed ALL of the medicine” =1
“Spat out SOME of the medicine” & “Spat out ALL of the medicine” and “Swallowed none” =2
“Vomited within 30 minutes after swallowing the medicine” = 3

Recode item 4

“Not enough liquid” & “Too much liquid” = 1
“Just enough liquid” = 2

Table 2.2 Scoring Matrix for the Palatability Questionnaire

Score	Q1 – Taste	Q3 – What happened	Q4 – Amount	Definition
0	Bad & Very bad; 2	Vomited < 30 min; 3	Not enough & too much; 1	Worst palatability
1	Bad & Very bad; 2	Vomited < 30 min; 3	Just enough; 2	1
2	Bad & Very bad; 2	Spat some/ all out; 2	Not enough & too much; 1	2
3	Bad & Very bad; 2	Spat some/ all out; 2	Just enough; 2	3
4	Bad & Very bad; 2	Swallowed all; 1	Not enough & too much 1	4
5	Bad & Very bad; 2	Swallowed all; 1	Just enough 2	5
6	V. good, Good & Not good/bad; 1	Vomited < 30 min; 3	Not enough & too much; 1	6
7	V. good, Good & Not good/bad; 1	Vomited < 30 min; 3	Just enough; 2	7
8	V. good, Good & Not good/bad; 1	Spat some/ all out; 2	Not enough & too much; 1	8

9	V. good, Good & Not good/bad; 1	Spat some/ all out; 2	Just enough; 2	9
10	V. good, Good & Not good/bad; 1	Swallowed all; 1	Not enough & too much; 1	10
11	V. good, Good & Not good/bad; 1	Swallowed all; 1	Just enough; 2	Best palatability

For the palatability questionnaire, standard descriptive analyses based on the derived scores will be provided at screening visit 1 (baseline), week 4, week 12, and EOT, as well as their changes from baseline at week 4, week 12, and EOT for patients pre-treated with deferasirox. For the Chelation naïve patients and patients treated with chelation therapy other than deferasirox who stopped chelation treatment more than 7 days prior to Screening visit, only descriptive statistics by visit will be provided. The standard descriptive analyses include: n, mean, standard deviation, minimum, median, and maximum. The 95% confidence intervals will be presented for the mean changes from baseline at week 4 and week 12 and EOT for patients pre-treated with deferasirox.

Box plot will be presented to summarize the scores graphically at week 4, week 12 and EOT.

2.13.3 GI symptom questionnaire

The GI symptom questionnaire consists of 6 items, 5 of which are scored using a 1-5 rating scale with appropriate end anchors to rate the symptom. The items are “Pains in the belly”, “Nausea (feeling like throwing up)”, “Vomiting”, “Constipation” and “Diarrhea”. All are scored as “Always”=5 (worst), “Most of the time”=4, “Sometimes”=3, “Rarely”=2, “Never”=1 (best).

The **sixth item** assesses bowel movement frequency during the past week, using 7 response options 0 = 0 (“None”), 1 = 1, 2 = 2, 3 = 3, 4 = 4, 5 = “5 – 10” and 6 = “11 or more”.

The GI symptoms questionnaire will be completed at all visits starting at screening visit 1 (excluding screening visit 2) until end of treatment. Response from GI symptom questionnaire at screening visit 1 will be considered as baseline.

A GI symptom score will be created as a summary score of all items (5 items), where a lower score represents a less severe GI symptom and a higher score represents a more severe GI symptom. **Item 6** will be excluded from the calculation of the weekly GI Symptom score; it will be used as a standalone item and will be presented descriptively using frequency counts.

The weekly average will be calculated when there are at least 4 non-missing daily responses by a subject. No additional imputation will be carried out.

GI symptoms will be summarized over time by descriptive statistics for all visits and for all patients (i.e. either Chelation naïve patients and patients treated with chelation therapy other than deferasirox who stopped chelation treatment more than 7 days prior to Screening visit or patients pre-treated with deferasirox). Descriptive statistics and the 95% confidence intervals

for the absolute mean changes by visit will be provided for patients pre-treated with deferasirox. The standard descriptive analyses include: n, mean, standard deviation, minimum, median, and maximum.

GI symptom scores as well as item 6 (bowel movement) will be summarized using descriptive statistics with the change from baseline to week 2, week3, week4, week 8, week 12, week 16, week 20 and EOT for patients pre-treated with deferasirox.

Box plot will be presented to summarize the scores graphically at week 2, week3, week4, week 8, week 12, week 16, week 20 and EOT.

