ICT naïve patients can adapt dose after 4 weeks on study. Dose adjustments for deferasirox FCT 3.5 mg or 7 mg/kg/day are to be tailored to the individual patient's response and the therapeutic goal of (reduction of iron burden). In patients not adequately controlled with deferasirox FCT doses of 21 mg/kg/day, doses of up to 28 mg/kg/day may be considered. The starting dose and the dose adjustment considerations must take into account that the therapeutic goal is reduction of iron burden (as opposed to maintenance of iron burden). Doses above 28 mg of deferasirox FCT

Recommended dose modifications for deferasirox

< 500 ng/ml	deferasirox FCT are required to maintain serum ferritin levels within the target range. Interruption of study treatment is required until serum ferritin rises above 500 ng/mL
Changes in urine protein/creatinine ratio	
> 0.5 (mg/mg) in two consecutive non- first void urine samples (a minimum of 48h apart), if all other causes of proteinuria have been excluded.	For patients who develop proteinuria or a worsening of pre-existing proteinuria at any visit, urine samples should be collected and assessed by the laboratory. In case of a single increase of the urinary protein/creatinine ratio the assessment should be repeated at the next visit. Deferasirox FCT dose reduction by 50% When resolution of UPCR (<0.5mg/mg) at the next study visit, dose can be resumed again at 100% If increase in UPCR >0.5mg/mg recurs again within 2 months after initial increase, therapy needs to be reduced to 50% of the last dose. If increase in UPCR does not recur after 2 months at reduced dose (50%), study medication can be returned to 100% of the last dose. Interrupt study treatment. When resolution of increase in UPCR (<0.5mg/mg) at the next study visit, dose can be resumed again at 50% of the last dose. If increase in UPCR does not recur after 1 month at reduced dose (50%), study medication can be returned to 100% of the last dose. Should proteinuria persist, study treatment may be discontinued if the investigator believes it is in the best interest of the patient. Novartis may be contacted by the investigator to discuss dosing options if the investigator so desires. Dose adjustment will be based on laboratory results.
> 1.0 (mg/mg) in one single non-first void urine samples.	
Severe skin reactions	

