¹ History of prior transfusion up to 3 months prior to Screening visit 1 (SV1) must be collected at SV1. Additionally, record of transfusion during the study must be collected.

² The choice of method for ocular and auditory assessments will be at the discretion of the investigators. Best efforts should be made to perform these assessments in all subjects, although feasibility in very young children will be at the discretion of the investigator.

³ Chelation naïve patients and patients treated with chelation therapy other than deferasirox who stopped chelation treatment more than 7 days prior to Screening visit 1 (SV1) will not complete questionnaires at SV1.

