7.2.8 Patient reported outcomes

As detailed in [Table 7-1](#) and provided in Appendix 14.1, patients or their caregivers will complete a series of ObsRO questionnaires at the study site (during study visits) as follows:

- palatability and mSCIT of crushed FCT, at SV1 and at the following visits: week 4, week 12 and at end of treatment
- gastrointestinal symptoms of crushed FCT at SV1 and at the following visits: week 2, week 3, week 4, week 8, week 12, week 16, week 20 and at end of treatment

Note: Chelation naïve patients and patients treated with chelation therapy who stopped treatment more than 7 days prior to Screening visit 1 will not complete questionnaires at screening.

8 Safety monitoring and reporting

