10.8 Sample size calculation

This study is designed to enroll a minimum of 40 patients. Statistical computations were performed (see table below) to evaluate probabilities to observe at least one patient with an AE given 40 patients and different scenarios of AE incidence rates (Hanely and Lippman- Hand 1983). This table shows a reasonable chance to observe AE events occurring with an incidence of 3% or higher together with the 95% Clopper-Pearson confidence interval (CI) for the incidence rate.

Table 10-1 Clopper-Pearson 95% CI for different incidence of AEs and the corresponding probability to observe at least one AE

Incidence of AE	Clopper-Pearson 95% CI for the incidence rate	Probability that at least one patient out of 40 experiences that AE
3%	(0.00, 0.14)	0.70
4%	(0.00, 0.15)	0.80
5%	(0.01, 0.17)	0.87
6%	(0.01, 0.18)	0.92
7%	(0.01, 0.20)	0.95
10%	(0.03, 0.24)	0.99
15%	(0.06, 0.30)	1.00
20%	(0.09, 0.36)	1.00
25%	(0.13, 0.41)	1.00
30%	(0.17, 0.47)	1.00

11 Ethical considerations and administrative procedures

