14.3 GI Symptom Questionnaire

Directions

Please read each symptom carefully. Indicate how often your child had each symptom **over the past week.**

Please answer all of the following questions about your child's GI symptoms after taking his/her medication for iron overload.

Items

1. Pain in his/her belly

- Always
- Most of the time
- Sometimes
- Rarely
- Never

2. Nausea (feeling like he/she might throw up)

- Always
- Most of the time
- Sometimes
- Rarely
- Never

3. Vomiting (throwing up)

- Always
- Most of the time
- Sometimes
- Rarely
- Never

4. Constipation

- Always
- Most of the time
- Sometimes
- Rarely
- Never

5. Diarrhea

- Always
- Most of the time
- Sometimes
- Rarely
- Never

6. How many bowel movements did your child have in the past week?

- 0 (none)
- 1
- 2
- 3
- 4
- 5-10
- 11 or more

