2.8.2.1 Statistical hypothesis test

No hypothesis will be tested for this primary endpoint.

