2.13.1.1 Adherence

Adherence domain will be captured from 2 perspectives:

- Child's perspective (a Domain score + a Checklist for reasons for non-adherence)
- Caregiver's perspective (a Domain score + a Checklist for reasons for non-adherence)

Even the adherence domain is divided into two perspective, all the items will be answered by the caregivers due to minors (2-6 years of age) enrolled in this study. First set of questionnaires will reflect about the child's devotion of taking the medicine and second set of questionnaires will reflect caregivers perspective of adherence for study medication. Out of 20 items of mSICT questionnaire, child's perspective domain scores consist of 6 items (Item: 3, 4, 5, 7, 8 and 9) while caregiver's perspective is captured by 6 items (Item: 13, 14, 15, 16, 18 and 19), i.e. overall 12 items will measure the adherence of the treatment.

Non-adherence items from the child perspective and caregiver's perspective domains consist of one item each (Item: 6) and (Item: 17) respectively.

Child's perspective of adherence:

Item 3 captures about the frequency of medicine intake and **item 5** discusses about how often child follows the doctor's instructions. **Items 3 and 5** will be measured using a 5-point response scale: "Always" =1 (best), "Most of the time" =2, "Sometimes" =3, "Rarely" =4 and "Never" =5(worst).

Item 4 discusses about how often the child express to stop the medication. The scale will be used to measure this as "Always" =5 (worst), "Most of the time" =4, "Sometimes" =3, "Rarely" =2, and "Never" =1 (best).

Two items (**Item 7 and 8**) use different response options. **Item 7** focuses on "How easy/hard did your child tell you it was to take his/her medicine" and uses the response scale "Very easy" =1 (best), "Easy" =2, "Neither easy or hard" =3, "Hard" =4, and "Very hard" =5 (worst). Similarly, **item 8** captures bother expressed by child for amount of time he/she had to wait to eat food after taking medication. The response scale for Item 8 will be "Very bothered" =5 (worst), "Quite Bothered" =4, "Moderately bothered" =3, "A little bothered" =2, and "Not bothered at all" =1 (best).

Item 9 reports “how happy your child appeared” and is scored on a scale from 1=Very happy (best) to 5=Very unhappy (worst).

[figure not shown]
Caregiver's perspective of Adherence:

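### The SAP scores questionnaires from weeks without drug during a directed interruption as if the child were on crushed tablets, and the screening rule for off-drug weeks is stated in two conflicting ways

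*SAP*

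**What the plan says.** Satisfaction, palatability and GI symptoms are a secondary objective, and the endpoint is the domain scores (Protocol Table 3-1). SAP 2.13 presents the three questionnaires as an evaluation of crushed tablets. All use a past-week recall, and the GI form asks "about your child's GI symptoms after taking his/her medication for iron overload" (Protocol 14.3).

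For SV1 the protocol recognises that a week without chelation cannot be rated. Protocol 7.2.8 says that chelation-naïve patients and "patients treated with chelation therapy who stopped treatment more than 7 days prior to Screening visit 1 will not complete questionnaires at screening"; 10.5.7 agrees. Footnote 3 to Table 7-1 narrows the second group to "patients treated with chelation therapy other than deferasirox who stopped chelation treatment more than 7 days prior to Screening visit 1", and SAP 2.13.1.3, 2.13.2 and 2.13.3 define their groups in the narrower way.

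After SV1 there is no corresponding rule. In SAP 2.13.3, "GI symptoms will be summarized over time by descriptive statistics for all visits and for all patients". mSICT and palatability are summarised at Week 4, Week 12 and end of treatment. Item 3, which "captures about the frequency of medicine intake" (SAP 2.13.1.1), and item 13, its caregiver counterpart, code *Never* as 5, the worst value.

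Interruptions are part of the plan. For ferritin below 500 ng/mL, Table 6-4 states: "Interruption of study treatment is required until serum ferritin rises above 500 ng/mL". Protocol 6.3.1.4 only recommends that interruption; the two texts must be reconciled. Other interruptions follow from urine protein/creatinine ratio, creatinine clearance, liver tests and rash (6.3.1.3, 6.3.1.5, 6.3.1.6.2, 6.3.1.7, Table 6-4).

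**The concern.** A child whose treatment is on hold still attends scheduled visits, and the caregiver still receives the form. The recall week then contains no crushed tablet to rate. The adherence items record obedience to the investigator as failure to take or give the drug, and the GI items describe a drug-free week. The affected children are selected by laboratory findings, rash or low ferritin, so the error is not random.

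Change-from-baseline confidence intervals are planned only for patients pre-treated with deferasirox. These patients may enter with ferritin just above 500 ng/mL (Protocol 5.2, criterion 4), close to the interruption threshold. Their SV1 baseline also depends on which of the two screening rules a site follows.

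**Working it through.** **The plan's own figures.** The plan gives no expected questionnaire score, standard deviation or interruption rate. Its only computed design figure is Table 10-1, for 40 patients. That reproduces (at 3% incidence, 1 − 0.97^40 = 0.704, stated as 0.70) but does not bear on this point. I take only the number of patients from it: "This study is designed to enroll a minimum of 40 patients" (Protocol 10.8).

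**1. Can a drug-free recall week meet a form?** Ferritin is measured monthly unless extra tests are done (Protocol 7.2.1), and from Week 4 the GI form is completed every four weeks. A ferritin interruption that lasts until the next scheduled measurement therefore covers the recall week of the next GI form. Exposure is lower for mSICT and palatability, which have three post-baseline visits against eight for GI. An interruption from after Week 4 to Week 8 touches neither.

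**2. Can the forms represent such a week?** No item in the adherence domains has an option for treatment stopped on medical advice, and the checklists in items 6 and 17 offer only *Other*. All four answers to palatability item 3 presuppose that a dose was put in the mouth. There is no valid palatability answer, so no size can be computed for that score.

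**3. Adherence, per child.** The child domain is items 3, 4, 5, 7, 8 and 9; the caregiver domain is items 13, 14, 15, 16, 18 and 19. Each item runs from 1 to 5, so the sum runs from 6 to 30. SAP 2.13.1.1 defines the score as a sum and 2.13.1.3 as a mean, so both are shown for the child domain.

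| Answers in the week | Sum | Mean |
|---|---|---|
| All best | 6 | 1.00 |
| Item 3 = 5, rest best | 10 | 1.67 |
| Items 3 and 5 = 5, rest best | 14 | 2.33 |
| Item 3 = 5; items 7, 8, 9 neutral (3) | 16 | 2.67 |

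The core effect is 5 − 1 = +4 on the sum, or 4/6 = +0.67 on the mean, if the on-drug answer would have been *Always*. The caregiver domain gives the same through item 13. The last two rows show what happens if caregivers also misread items with no sensible off-drug answer.

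**4. Adherence, visit mean.** Shift = share interrupted × 0.67. At 5% this is 0.03; at 20% it is 0.13 (shares assumed).

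**5. GI score.** I read the five-item summary score as a sum, range 5 to 25. If symptoms stop off drug, the score is 5 × 1 = 5, the best possible. With an assumed on-drug sum of 6 to 10, each affected child falls by 1 to 5 points. Shift in the visit mean = (number interrupted / 40) × fall:
- 1 of 40, fall of 1: 0.025, about 0.03
- 8 of 40, fall of 5: 1.0

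**6. SV1 rule.** Take a deferasirox child off drug for more than seven days. Under 7.2.8 and 10.5.7 no SV1 form is completed, so there is no baseline. Under footnote 3 and the SAP groups the child completes the form and supplies an off-drug baseline for the change analysis. Both cannot be followed. No assumption is needed to see this.

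**The case against.** Protocol 10.5.7 itself asks for GI summaries at all visits and in all patients, so the SAP follows its parent document. Describing scores regardless of interruption is a legitimate choice of estimand, and removing interrupted children could itself flatter the crushed tablets. For the GI score this stands, and neither summary should displace the other. It does not rescue the adherence score, where following an instruction is coded as not taking the drug, nor palatability, where there was nothing to taste.

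Three stronger readings are tempting, and the documents do not support them.

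- *A directed interruption makes adherence look worst.* This is true of one item in each six-item domain, not of the domain score, which is the endpoint. The same family can answer *Always* (1, best) to items 5 and 15 on following the doctor's instructions.
- *It produces a large false relief of GI symptoms.* A record with three symptoms *Sometimes* (sum 11) falling to 5 would show 6 points, but that record is hand-picked. The interruptions named above are not for GI symptoms. Nor need symptoms stop off drug: in the earlier paediatric studies fewer than half of the patients with GI disorders had them attributed to treatment (Protocol 1.2).
- *Early stoppers are affected in the same way.* Their end-of-treatment visit falls within seven days of stopping (Protocol 4.1, 7.1.5), so the recall week normally contains a dose. They are not part of this point.

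The SV1 conflict may touch few children, since deferasirox patients need no washout. It remains a contradiction between current texts.

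**Conclusion.** The point holds in limited form. SAP 2.13 has no rule for a recall week that is drug-free by instruction, although the protocol applies that logic at SV1. The adherence effect is a wrong score for each affected child, but a small shift in the visit mean if only items 3 and 13 are affected. The GI effect ranges from negligible to about one point on a 5-to-25 scale. It rests on three assumptions that the documents cannot settle: how many children are interrupted at a visit, their on-drug scores, and whether symptoms stop off drug. The SV1 inconsistency is certain; its frequency is unknown.

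The consequences are confined to descriptive secondary summaries. The primary endpoint comes from the adverse event pages (SAP 2.8.1), where "No hypothesis will be tested for this primary endpoint", and is unaffected. The change is worth making because it is cheap and corrects scores that would otherwise be wrong.

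**What to change.** In SAP 2.13:

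1. Flag each post-baseline form whose whole seven-day recall lies inside a directed interruption. Use the Dosage Administration CRF dates and the recorded reason for interruption, which SAP 2.6.4 already uses. State whether interruptions that are recommended, and not only those required, count as directed.
2. Leave flagged forms out of the adherence and palatability scores. Keep weeks missed through non-compliance in the adherence score, because that is what it should measure.
3. For the GI score, show on-drug and all-forms summaries side by side.
4. List the flagged forms.

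Apply one SV1 rule to all chelators, and align Table 7-1 footnote 3 and the SAP group definitions with Protocol 7.2.8 and 10.5.7.

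The cost is SAP wording, a protocol footnote correction, one derived flag from data already collected, one extra table and slightly fewer forms at some visits.
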